5.4. PROTOCOL DEVIATIONS

Any deviation from protocol will be listed by subject and date. The type of deviation along with a description and any additional comments about the deviation will be listed.

In cases where the statistical analysis plan differs from the protocol, the statistical analysis plan will supersede the protocol.

6. CHANGES IN THE PLANNED ANALYSES

An analysis of the number of doses of antipyretic medications will be prepared.

There are no further changes anticipated to the protocol specified analyses. Should any more deviations occur, these changes will be fully described in the Clinical and Statistical Report.

7. REVISION HISTORY

Date	Revision	Rationale
-------------	-----------------	------------------

8. PROGRAMMING CONVENTIONS

- Page orientation, margins, and fonts: Summary tables, listings, and figures will appear in landscape orientation. There should be a minimum of a 1.25" boundary on the upper (bound) edge, and a minimum of a 1.0" boundary on the remaining three edges. Output should be printed in Courier New with a point size of 8. Titles may be printed using a larger font (eg, Arial point size 10).
- Identification of analysis population: Every summary table and figure should clearly specify the analysis population being summarized. All listings will be prepared for all subjects enrolled.
- Group headers: In the summary tables, the group headers will identify the age group and the within-group sample size for the indicated analysis population. Of note, the header's sample size does not necessarily equal the number of subjects actually summarized within any given summary module; some subjects in the analysis population may have missing values and thus may not be summarized.
- Suppression of percentages corresponding to null categories: When count data are presented as category frequencies and corresponding percentages, the percent should be suppressed when the count is zero in order to draw attention to the non-zero counts.
- Presentation of sample sizes: Summary modules should indicate, in one way or another, the number of subjects actually contributing to the summary statistics presented in any given summary module. As mentioned above, this may be less than the number of subjects in the analysis population.
 - ◆ In the quantitative modules describing continuous variables (and thus presenting sample size, means, and standard deviations), the sample size should be the number of non-missing observations
 - ◆ For categorical variables that are presented in frequency tables, the module should present the total count in addition to the count in each category. Percentages should be calculated using this total as the denominator, and the percentage corresponding to the sum itself (that is, 100%) should be presented so as to indicate clearly to a reviewer the method of calculation.
- Sorting: Listings will be sorted by age group, subject number and date, if applicable. If a listing is sorted in a different manner, a footnote will indicate as such.
- General formatting rules: Rounding for all variables will occur only as the last step, immediately prior to presentation in listings, tables, and figures. No intermediate rounding will be performed on derived variables. The standard rounding practice of rounding numbers ending in 0-4 down and numbers ending in 5-9 up will be employed.
- The presentation of numerical values will adhere to the following guidelines:

- ◆ Raw measurements will be reported to the number of significant digits as captured electronically or on the CRFs.
- ◆ Standard deviations will be reported to one decimal place beyond the number of decimal places the original parameter is presented.
- ◆ Means will be reported to the same number of significant digits as the parameter.
- ◆ Calculated percentages will be reported with no decimals.
- Dates will be formatted as DDMMYYYY. Partial dates will be presented on data listings as recorded on CRFs.
- Time will be presented according to the 24-hour clock (HH:MM).

9. PROPOSED TABLES, LISTINGS, AND FIGURES FOR FINAL ANALYSIS

Output Number	Output Title
Table 14.1.1	Subject Follow-Up and Termination from Study: Intent-to-Treat Population
Table 14.1.2.1	Eligibility and Treatment Status: Intent-to-Treat Population
Figure 14.1.2.2	BCX1812-306 Study Population Disposition: Intent-to-Treat Population
Table 14.1.3	Populations for Analysis: Intent-to-Treat Population
Table 14.1.4.1	Demographics and Baseline Characteristics: Intent-to-Treat Population
Table 14.1.4.2	Demographics and Baseline Characteristics: Intent-to-Treat Infected Population
Table 14.1.4.3	Demographics and Baseline Characteristics: Safety Population
Table 14.1.4.4	Demographics and Baseline Characteristics: Exposure-Response Population
Table 14.1.5	Summary of Subject Diary Completion: Intent-to-Treat-Infected Population
Table 14.2.1.1	Summary of Oral Temperature Diary Assessments (°C): Intent-to-Treat Infected Population
Table 14.2.1.2	Time to Resolution of Fever: Intent-to-Treat Infected Population
Table 14.2.1.2.X	Time to Resolution of Fever: Viral Subtype: Intent-to-Treat Infected Population
Figure 14.2.1.3	Time to Resolution of Fever (Kaplan-Meier Plot): ITTI Population
Figure 14.2.1.4	Median (95% CI) Time to Resolution of Fever: ITTI Population
Figure 14.2.1.5	Box Plots of Time to Resolution of Fever: ITTI Population
Table 14.2.2.1	Time to Alleviation of Symptoms: Intent-to-Treat Infected Population

Output Number	Output Title
Table 14.2.2.1.X	Time to Alleviation of Symptoms: Viral Subtype: Intent-to-Treat Infected Population
Figure 14.2.2.2	Time to Alleviation of Symptoms (Kaplan-Meier Plot): ITTI Population
Figure 14.2.2.3	Median (95% CI) Time to Alleviation of Symptoms: ITTI Population
Figure 14.2.2.4	Box Plots of Time to Alleviation of Symptoms: ITTI Population
Table 14.2.3.1	Summary of Changes \log_{10} Tissue Culture Infective Dose ₅₀ (TCID ₅₀ /mL) by Study Visit: Subjects with Positive Baseline Titers; Intent-to-Treat Infected Population
Table 14.2.3.1.X	Summary of Changes \log_{10} Tissue Culture Infective Dose ₅₀ (TCID ₅₀ /mL) by Study Visit: Subjects with Positive Baseline Titers: Viral Subtype: Intent-to-Treat Infected Population
Figure 14.2.3.2	Box Plots of Viral Titers (TCID ₅₀ /mL) by Study Visit; Subjects with Positive Baseline Titers: Intent-to-Treat Infected Population
Figure 14.2.3.3	Histograms of Viral Titers (TCID ₅₀ /mL) by Study Visit; Subjects with Positive Baseline Titers: Intent-to-Treat Infected Population
Figure 14.2.3.4	Median (with IQR) Change from Baseline Viral Titers (TCID ₅₀ /mL) by Study Visit: Subjects with Positive Baseline Titers: Intent-to-Treat Infected Population
Table 14.2.4.1	Summary of Viral Shedding by Study Visit; Subjects with Positive Baseline Titers: Intent-to-Treat Infected Population
Table 14.2.4.1.X	Summary of Viral Shedding by Study Visit: Subjects with Positive Baseline Titers: Viral Subtype: Intent-to-Treat Infected Population
Table 14.2.5.1	Summary of RT-PCR Result by Study Visit: Subjects with Positive Baseline RT-PCR: Intent-to-Treat Infected Population
Table 14.2.5.1.X	Summary of RT-PCR Result by Study Visit: Subjects with Positive Baseline RT-PCR: Viral Subtype: Intent-to-Treat Infected Population

Output Number	Output Title
Table 14.2.6	Change of Influenza Virus Susceptibility to Neuraminidase Inhibitors: Intent-to-Treat Infected Population
Table 14.2.7	Summary of Influenza-Related Complications and Hospitalizations: Intent-to-Treat Infected Population
Table 14.2.8	Number of Doses of Antipyretic Medications: Intent-to-Treat Infected Population
Table 14.2.9.1	Summary of Subject-Rated Assessment of Ability to Perform Daily Activities: Intent-to-Treat Infected Population
Table 14.2.9.2	Time to Return to Usual Activities: Intent-to-Treat Infected Population
Table 14.3.1.1	Overall Summary of Treatment-Emergent Adverse Events: Safety Population
Table 14.3.1.2	Treatment-Emergent Adverse Events by System Organ Classification, Preferred Term and Greatest Severity: Safety Population
Table 14.3.1.3	Treatment-Emergent Adverse Events by System Organ Classification and Preferred Term: Safety Population
Table 14.3.1.4	Treatment-Emergent Adverse Events Possibly, Probably, or Definitely Related to Study Drug by System Organ Classification and Preferred Term: Safety Population
Table 14.3.1.5	Treatment-Emergent Serious Adverse Events by System Organ Classification and Preferred Term: Safety Population
Table 14.3.1.6	Treatment-Emergent Adverse Events Leading to the Discontinuation of Study by System Organ Classification and Preferred Term: Safety Population
Table 14.3.1.7	Treatment-Emergent Adverse Events Leading to the Discontinuation of Study Drug by System Organ Classification and Preferred Term: Safety Population
Table 14.3.1.8	Treatment-Emergent Adverse Events Occurring in $\geq 10\%$ of Subjects by Preferred Term: Safety Population

Output Number	Output Title
Table 14.3.4.1.1	Summary of Chemistry Laboratory Values by Study Visit: Safety Population
Table 14.3.4.1.2	Summary of Hematology Laboratory Values by Study Visit: Safety Population
Table 14.3.4.2	Graded Laboratory Toxicities: Safety Population
Table 14.3.4.3.1	Laboratory Shifts from Baseline to Day 7 - Chemistry: Safety Population
Table 14.3.4.3.2	Laboratory Shifts from Baseline to Day 7 - Hematology: Safety Population
Table 14.3.4.3.3	Laboratory Shifts from Baseline to Day 7 - Urinalysis: Safety Population
Table 14.3.5	Study Drug Exposure: Safety Population
Table 14.3.6	Summary of Vital Signs by Study Visit: Safety Population
Table 14.3.7.1	Concomitant Medications by Generic Name and Drug Classification: Safety Population
Table 14.3.7.2	Antipyretic Concomitant Medications by Generic Name and Drug Classification: Safety Population
Table 14.3.7.3	Concomitant Medications Used to Treat Influenza Symptoms by Generic Name and Drug Classification: Safety Population
Table 14.4.1.1	Summary of Plasma Concentrations of Peramivir by Time Point: Intent-to-Treat Population
Table 14.4.1.2	Summary of Plasma Concentrations of Peramivir by Time Point: Exposure-Response Population
Figure 14.4.2	Relationship between Time to Alleviation of Influenza Symptoms and Peramivir Plasma Concentrations at 30-60 Minutes Post-Dose: Exposure-Response Population

Output Number	Output Title
Figure 14.4.3	Relationship between Viral Change from Baseline and Peramivir Plasma Concentrations at 30-60 Minutes Post-Dose: Exposure-Response Population
Listing 16.2.1	Study Completion: Intent-to-Treat Population
Listing 16.2.2	Protocol Deviations: Intent-to-Treat Population
Listing 16.2.4.1	Inclusion/Exclusion Criteria: Intent-to-Treat Population
Listing 16.2.4.2	Subject Eligibility: Intent-to-Treat Population
Listing 16.2.4.3	Demographics: Intent-to-Treat Population
Listing 16.2.4.4	Medical History: Intent-to-Treat Population
Listing 16.2.4.5	Prior and Concomitant Medications: Intent-to-Treat Population
Listing 16.2.5.1	Study Medication Administration: Intent-to-Treat Population
Listing 16.2.5.2	Pharmacokinetic Sample Collection Time and Concentrations: PK Population
Listing 16.2.6.1.1	Summary of Efficacy Variables: Intent-to-Treat-Infected Population
Listing 16.2.6.2	Influenza Symptoms: Intent-to-Treat Population
Listing 16.2.6.3	Temperature: Intent-to-Treat Population
Listing 16.2.6.4	Subject-Rated Assessment of Daily Activities and Assessment of Appetite and Eating Patterns: Intent-to-Treat Population
Listing 16.2.6.5	Viral Titers and Viral Susceptibility: Intent-to-Treat Population
Listing 16.2.6.6	Symptom Relief Medications: Intent-to-Treat Population
Listing 16.2.6.7	Influenza-Related Complications: Intent-to-Treat Population
Listing 16.2.7.1	Adverse Events: Intent-to-Treat Population
Listing 16.2.7.2	Serious Adverse Events: Intent-to-Treat Population

Output Number	Output Title
Listing 16.2.8.1.1	Laboratory Tests - Hematology: Intent-to-Treat Population
Listing 16.2.8.1.2	Laboratory Tests - Chemistry: Intent-to-Treat Population
Listing 16.2.8.1.3	Laboratory Tests - Urinalysis: Intent-to-Treat Population
Listing 16.2.8.2	Blood and Urine Collection and Pregnancy Tests: Intent-to-Treat Population
Listing 16.2.8.3	Virology Specimen Collection and Influenza Antibodies Analysis: Intent-to-Treat Population
Listing 16.2.8.4	Vital Signs, Height, and Weight: Intent-to-Treat Population
Listing 16.2.8.5	Physical Examinations: Intent-to-Treat Population

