3.3.8. Definitions and Terminology

Age

Age will be defined as the age in years at time of signing of informed consent for all subjects.

Confirmed Influenza

A subject will be confirmed as having acute influenza infection if any specimen for assay of influenza A or B antigen by RT-PCR obtained during the study is positive.

Baseline Value

For purposes of analysis, the baseline value is defined as the last value obtained prior to initiation of study drug (eg, the Baseline Pre-Dose value). Should this value be obtained after the injection of study drug, then the most recent value obtained prior to initiation of study drug will be used for the baseline value.

Day 1

Day 1 is the day/time that study drug is initiated.

Study Day

Study Day is defined relative to Baseline (Day 1). Thus, the study day of an event is calculated as:
Study Day = event date – date of Day 1 +1.

Days on Study

Days on Study is the number of days from Day 1 to the date of study completion or early termination as recorded on the Day 14/End of Study/Early Withdrawal CRF.

Days of Subject Diary Completion

Days of Subject Diary Completion is defined as the number of days from Day 1 to the date of last Subject Diary completion. For the purposes of this analysis, the date of last Subject Diary completion is defined as the last date in which the Subject Diary had at least one complete assessment of symptoms recorded.

Alleviation of Symptoms

A subject has Alleviation of Symptoms if all of the assessed symptoms of influenza assessed on his/her subject diary are either absent or are present at no more than mild severity level and at this status for a 21.5 hour period (24 hours less 10%).

Composite Symptom Score

The Composite Symptom Score is defined as the sum of the seven symptoms of influenza (cough, sore throat, stuffy nose, muscle aches, headache, feverishness, fatigue/tired) assessed on a given time point within the subject diary.

Baseline Composite Symptom Score

The Baseline Composite Symptom Score is defined as the sum of the symptoms of influenza recorded by the subject in the diary corresponding to the assessment of a subject's symptoms prior to the initiation of study drug.

Resolution of Fever

A subject has Resolution of Fever if he/she has a temperature < 37.4°C/99.4°F oral and no antipyretic medications have been taken for at least 12 hours. Resolution of Fever is based on information obtained from the individual subject diaries.

Ability to Perform Usual Activities

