4.2. INTENT-TO-TREAT INFECTED POPULATION

The ITTI population will include all subjects who are enrolled, treated, and have influenza type A or B confirmed by PCR. The ITTI population will be used for analyses of effectiveness.

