4.4. EXPOSURE-RESPONSE POPULATION

The exposure-response population will include all subjects in the ITTI population who have a quantifiable peramivir concentration on Day 1 and have at least one post-baseline effectiveness assessment. This population will be used for all exposure-response analyses.

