5.2.2. Effectiveness Analyses

A subject's oral temperature taken by subjects and recorded in the diary by subjects/caregivers will be summarized by age group and overall by study visit. A subject has Resolution of Fever if he/she has an oral temperature $< 37.4^{\circ}\text{C}/99.4^{\circ}\text{F}$ oral and no antipyretic medications have been taken for at least 12 hours. The time to resolution of fever will be estimated for each age group and overall using the Kaplan-Meier method with temperature and symptom relief medication information obtained from the subject diary data. Subjects who do not have resolution of fever will be censored at the time of their last non-missing post-baseline temperature assessment.

Alleviation of symptoms will be determined by assessment of symptoms as reported on each Subject Diary. The time to alleviation of symptoms, defined as the time from initiation of study drug until the start of the 21.5 hour period (24 hours less 10%) where all symptoms of influenza are recorded as none or mild, will be estimated overall and for each age group using the Kaplan-Meier method. Subjects who do not experience alleviation of symptoms will be censored at the date of their last non-missing post-baseline assessment.

Change from baseline in \log_{10} TCID₅₀/mL through Day 3, Day 7, and Day 14 will be presented by age group and overall for subjects with positive viral titers at baseline (\log_{10} TCID₅₀/mL > 0.5). A box plot and a histogram of the TCID₅₀/mL values will be presented by visit and age group. In addition, the median change from baseline in TCID₅₀/mL will be presented by visit and age group.

The number and percent of subjects with positive viral titers at baseline (\log_{10} TCID₅₀/mL > 0.5) that shed virus at each visit will be presented by age group and overall.

The RT-PCR results at each visit will be presented by age group and overall for subjects with positive RT-PCR results at baseline.

Change from baseline to last positive value of influenza virus susceptibility to neuraminidase inhibitors will be assessed using virology laboratory tests. Virology laboratory tests will include phenotypic characterizations of influenza virus recovered (hemagglutinin and neuraminidase) and viral susceptibility to zanamivir, oseltamivir, and peramivir, as well as genotyping of virus isolates. These analyses will be presented overall and by age group and viral subtype.

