5.2.3. Exploratory Exposure Response Analyses

Summaries of plasma concentrations of peramivir will be presented by time point and age group. Scatter plots will be generated for time to alleviation of influenza symptoms and change from baseline in \log_{10} TCID₅₀/mL versus peramivir plasma concentration at 30-60 minutes following study drug administration. The data from this trial together with data from prior trials may be used to complete a separate exposure-response analysis. The methods for the exposure-response analysis will be presented in a separate Statistical Analysis Plan.

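### The viral exposure-response plot (SAP 5.2.3, Figure 14.4.3) does not carry the positive-baseline-titre restriction used in every other titre-change table and figure, and names no visit

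*SAP*

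**What the plan says.** SAP 5.2.3 plans scatter plots of two outcomes, time to alleviation of symptoms and change from baseline in log10 TCID50/mL, "versus peramivir plasma concentration at 30-60 minutes following study drug administration". It sets no baseline-titre condition and names no visit. The viral plot is listed in SAP Section 9 as Figure 14.4.3: "Relationship between Viral Change from Baseline and Peramivir Plasma Concentrations at 30-60 Minutes Post-Dose: Exposure-Response Population".

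The named population is defined in SAP 4.4: "The exposure-response population will include all subjects in the ITTI population who have a quantifiable peramivir concentration on Day 1", with at least one post-baseline effectiveness assessment. The ITTI definition in SAP 4.2 is: "The ITTI population will include all subjects who are enrolled, treated, and have influenza type A or B confirmed by PCR". Under SAP 3.3.8, influenza is confirmed if "any specimen for assay of influenza A or B antigen by RT-PCR obtained during the study is positive". None of these definitions requires a positive culture, at baseline or later.

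The main titre analysis differs. SAP 5.2.2 says that change from baseline in log10 TCID50/mL through Days 3, 7 and 14 "will be presented by age group and overall for subjects with positive viral titers at baseline", meaning above 0.5. The restriction is repeated in the output titles; Figure 14.2.3.4, for example, ends "by Study Visit: Subjects with Positive Baseline Titers: Intent-to-Treat Infected Population".

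**The concern.** One variable, change in log10 TCID50/mL, is handled in two ways. The tables and figures that describe it exclude subjects without a positive baseline titre. The plot that relates it to exposure, as titled, does not. A subject who is PCR-positive but culture-negative at baseline has little or no measurable titre to lose, so that subject's change says little about response to the drug at any concentration. Plotted with the rest, such subjects look like non-responders.

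Figures 14.4.2 and 14.4.3 are the only two displays in the SAP that relate an outcome to concentration. The pooled exposure-response analysis is left to a separate plan: Protocol 13.10 says that the data will be used for it, SAP 5.2.3 only that they may be. What is at stake is how the viral plot is read, and whether it rests on the same subjects as Table 14.2.3.1. Because no visit is named, plots for Day 3, Day 7 or Day 14 would all satisfy the text.

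**Working it through.** The plan states no figure on this point, so there is none to reproduce. The check sets the texts side by side and then works through what the missing restriction does.

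**1. The texts compared**

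| Output | Population in title | Baseline restriction in title |
|---|---|---|
| Tables 14.2.3.1 and 14.2.3.1.X, Figures 14.2.3.2 to 14.2.3.4 (titre and titre change) | ITTI | positive baseline titre |
| Tables 14.2.4.1 and 14.2.4.1.X (shedding) | ITTI | positive baseline titre |
| Tables 14.2.5.1 and 14.2.5.1.X (RT-PCR) | ITTI | positive baseline RT-PCR |
| Figure 14.4.3 (titre change against concentration) | Exposure-response | none |

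The SAP writes the restriction into each title where it applies, and SAP Section 8 asks every table and figure to specify its analysis population clearly. Protocol 13.8.2 has no baseline-titre condition that could fill the gap.

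**2. If baseline culture status is independent of concentration**

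Let f be the culture-negative fraction of plotted subjects, with change taken as 0. In the others, let the change have mean μ, SD s and correlation r0 with concentration. Then:

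- pooled slope = (1 − f) × slope in culture-positive subjects
- pooled r = (1 − f) r0 s / √[(1 − f)s² + f(1 − f)μ²]

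All of f, μ, s and r0 are assumptions. With μ = −2, s = 1, r0 = −0.5 and f = 0.2: r = −0.40 / √(0.80 + 0.64) = −0.40 / 1.20 = −0.33. With r0 = −0.5 throughout:

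| f | Slope multiplier | r (μ −2, s 1) | r (μ −2, s 1.5) | r (μ −1, s 1) |
|---|---|---|---|---|
| 0 | 1.0 | −0.50 | −0.50 | −0.50 |
| 10% | 0.9 | −0.40 | −0.44 | −0.45 |
| 20% | 0.8 | −0.33 | −0.38 | −0.41 |
| 40% | 0.6 | −0.24 | −0.30 | −0.33 |
| 50% | 0.5 | −0.20 | −0.26 | −0.29 |

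**3. If they are not independent**

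Independence is not assured. Dose depends on creatinine clearance (600, 200 or 100 mg, Protocol Table 2), and presentation later than 48 hours is allowed for about 20% of elderly subjects only (Protocol 8.1). Let concentration have within-group SD 1, let culture-negative subjects differ in mean concentration by d, and let β be the slope in culture-positive subjects. Then:

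pooled slope = [(1 − f)β − f(1 − f)dμ] / [1 + f(1 − f)d²]

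With μ = −2:

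| β | f | d = +0.5 | d = −0.5 |
|---|---|---|---|
| 0 | 20% | 0.16/1.04 = +0.15 | −0.16/1.04 = −0.15 |
| 0 | 40% | 0.24/1.06 = +0.23 | −0.24/1.06 = −0.23 |
| −0.5 | 20% | (−0.40 + 0.16)/1.04 = −0.23 | (−0.40 − 0.16)/1.04 = −0.54 |
| −0.5 | 40% | (−0.30 + 0.24)/1.06 = −0.06 | (−0.30 − 0.24)/1.06 = −0.51 |

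A true relation can be nearly hidden or slightly exaggerated, and a relation can appear where there is none.

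**4. With the restriction**

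Setting f = 0 returns slope β and correlation r0 in both cases.

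**The case against.** The strongest reply is that the SAP is silent rather than wrong. SAP 5.2.2 gives the rule for change in log10 TCID50/mL, 5.2.3 plots the same variable, and the Section 9 outputs are only proposed, so a programmer could carry the rule over. A reader might therefore go too far in inferring that the sponsor chose to include culture-negative subjects; the documents show an omission, not a decision. The omission still matters, because the other titles all state the restriction and this one does not.

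A reader might also infer that the plot must flatten the relation and lead to a false finding of no exposure-response. The documents do not support that. Dilution follows only under independence, and step 3 shows that the error can run either way. Nor does the SAP give a detection limit or a rule for titres at or below 0.5, so treating that cut as a floor is an assumption, and such titres could still rise. That most titres would be at the floor by later visits is likewise not documented.

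Three further points stand. The plot is exploratory, SAP Section 5 plans no hypothesis testing, and no slope, correlation or mean is planned for this figure, so no reported estimate would be biased or contradict the main titre results. Subjects with no change might also show as a visible band at zero. And SAP 5.1 tabulates baseline viral titre status for this population (Table 14.1.4.4), so readers would be able to see the culture-negative fraction.

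**Conclusion.** The point holds as a gap in the specification of one exploratory figure. Followed as written, Figure 14.4.3 admits PCR-confirmed subjects without a positive baseline titre, rests on a different baseline criterion from Table 14.2.3.1, and leaves the visit open. If culture status is independent of concentration, the underlying slope shrinks by the factor 1 − f; if not, the distortion may go either way. The size in this trial is unknown: f is not given, and every effect size above rests on assumed inputs and on a change of zero in culture-negative subjects. Neither the primary safety objective nor any table is affected. The correction is worth making because it costs almost nothing and applies a rule that the SAP already has.

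**What to change.** Add the positive-baseline-titre restriction (log10 TCID50/mL > 0.5), worded as in the title of Table 14.2.3.1, to the viral scatter plot in SAP 5.2.3 and to the title of Figure 14.4.3. In both places name the visit or visits plotted, consistent with SAP 5.2.2: either Day 3 alone, or one panel each for Days 3, 7 and 14. Both choices fit the existing text.

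Marking baseline titre by plotting symbol is optional. No new listing is needed, because the excluded subjects can be identified from Listing 16.2.6.5. The cost is a short text edit and a filter in one program, with no new data. The downside is fewer points in one exploratory figure.
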